5.2.3 Experimental Sessions (Visit 4 and 8)

Subjects in Stage 1 will receive two double-blind experimental sessions of MDMA-assisted psychotherapy scheduled approximately 3-5 weeks apart, and subjects in the open label leadin and open label Stage 2 will receive two experimental sessions with the full dose of MDMA. Procedures for MDMA-assisted psychotherapy will remain the same across all sessions, and all procedures except the drug received will be the same.

- a. At least 24 hours prior to the first experimental session the subject will be randomized. The therapist team conducting the session will obtain the container assignment using a web-based randomization program prior to the session.
- b. On the day of the experimental session, the subject will arrive approximately 1-1.5 hours prior to drug administration.
- c. Confirm continuing eligibility by reviewing inclusion/exclusion criteria.
- d. Perform a urine drug screen. A positive drug screen will be reviewed by the investigator and may be cause for delaying drug administration to a later time, rescheduling the session to a later date, or withdrawing the subject from the study.
- e. If a woman is of childbearing potential, perform a urine pregnancy test. A positive pregnancy screen is cause for withdrawal from the protocol.
- f. If the subject continues to meet criteria and the subject reports that he/she followed appropriate rules and restrictions, the session will proceed.
- g. Review procedures for the experimental session with the subject.
- h. Record the entire session to video and audio. Subjects may receive a copy of audio or video recordings of their experimental sessions upon request.
- i. The session will last for approximately eight hours or longer, followed by an overnight stay at the study site.
- j. The subject will complete the C-SSRS approximately one hour to a half hour prior to drug administration.

Table 4. Schedule of procedures and measures for experimental sessions.

Approximate Time	Procedure or Action
9:00	Urine drug screen and pregnancy test. Subject acclimated to
0.45	environment, C-SSRS
9:45	Baseline BP, Pulse, Subjective Units of Distress Rating (SUD)
9:55	2 nd Baseline BP, Pulse, Body Temperature (BT), SUD
10:00	MDMA Administration, begin recording to audio and video
10:30	BP, Pulse
11:00	BP, Pulse, SUD, BT
11:30	BP, Pulse; Can administer optional supplemental dose
12:00	BP, Pulse, BT
12:30	BP, Pulse, SUD
13:00	BP, Pulse
13:30	BP, Pulse, BT
14:00	BP, Pulse, SUD

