Every hour, and as	BP, Pulse
needed	
Every 60-90 minutes	SUD, BT
Approximately 6	C-SSRS, General Wellbeing
hours after drug	
administration	

- k. Before drug administration, discuss and review the subject's goals, intentions and concerns and some of the commonly experienced effects of MDMA.
- 1. Instruct the subject not to use caffeine or nicotine 1 hour before or 3 hours after the dose of drug.
- m. Subject body temperature will be measured 15 and 5 minutes prior to initial dose administration and approximately every hour after that. The therapists may make more frequent measurements if body temperature exceeds more than 1°C above baseline.
- n. Subjects will complete the SUD 15 and 5 minutes prior to initial dose administration. Subjects will complete the SUD every 60 to 90 minutes, until the session is over, allowing a window of up to 30 minutes to fit into the psychotherapy process where a natural break occurs. If necessary, the therapists can make a greater number of measurements as their clinical judgment dictates.
- o. Measure blood pressure and pulse 15 and 5 minutes prior the experimental session, and once every half-hour throughout the experimental session if the established thresholds for normal blood pressure and pulse have not been exceeded for the duration of the experimental session. More frequent measures will be taken if the established thresholds of 160 systolic, 110 diastolic or pulse 110 are exceeded. Measurements should be taken every 5 minutes until the values fall below these levels or until they have been decreasing for 15 minutes or have stabilized at a level judged by the investigator to be safe. The therapists may also make more frequent measurements if a subject exhibits symptoms indicative of hypertension.
- p. At approximately 10:00 in the morning, subjects will receive the initial dose of drug along with a glass of water.
- q. The subject will sit or recline on comfortable furnishings. Eyeshades and a program of music will be provided if the subject wishes to use them. Subjects will listen to a program of music designed to support their experience by initially aiding relaxation and later evoking and supporting deep emotions and the emergence of unconscious material [77-79]. Subjects may speak to the therapists whenever they wish, who will provide guidance and support as needed.

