- r. After the first hour, if the subject has not spoken spontaneously, check in with him/her about the nature of the experience. For the rest of the experience, as appropriate, the therapists will support and encourage the subject in emotional processing and resolution of whatever psychological material is emerging.
- s. Record any spontaneously reported reactions during the session.
- t. Provide water and electrolyte containing fluids throughout the session but not to exceed 3 L overall.

- u. A supplemental dose half the size of the initial dose may be administered approximately 1.5 to 2.5 hours after the initial dose upon mutual agreement between the therapists and subject.
- v. Provide food during the latter part of the session.
- w. If there is a support-individual who has previously been asked and has agreed to be present during part or all of the MDMA session, that person may arrive during the session at whatever time has been agreed upon, but will wait in the waiting room until brought back to the session room by one of the therapists. The support person may arrive after the session has ended.
- x. If it is appropriate to do so, initiate the first question of the C-SSRS at any point in the session if the subject is experiencing significant psychological distress that does not respond readily to processing with the therapists according to the methods described in the MDMA-assisted psychotherapy treatment manual.
- y. End the session if all medical and psychiatric parameters are acceptable and the subject is alert, ambulatory and emotionally stable.
- z. The therapists will depart the site when they have concluded that the subject is emotionally and medically stable. Therapists shall remain available to subjects during the experimental session and for one week after via 24-hour cellular phone.
- aa. Spontaneously reported reactions, AEs and Medications will be collected as described in Sections 8.5 and 9.0 of the protocol.

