7.2.1 Cardiovascular and Sympathomimetic Effects

The full dose of 125 mg, followed by a supplemental dose of 62.5 mg after 1.5 to 2.5 hours, is expected to produce significant but transient, self-limited increases in blood pressure and heart rate. These changes should last no more than six hours. In less than 5% of volunteers in Phase 1 studies, increases in blood pressure were higher than 140/90 mmHg. Clinical intervention was not required in any of these cases. Nonetheless, careful monitoring of participants and predefined contingency plans will allow the researchers to rapidly identify and manage any related toxicity. For more information, see the Investigator's Brochure.

Risks posed by elevated blood pressure will be addressed by excluding people with hypertension and monitoring blood pressure and pulse as described in Safety Measures section 5.1.2. During experimental sessions the co-therapists will continually evaluate the patient for increasing blood pressure and signs or symptoms of a developing hypertensive or other cardiovascular emergency. Subjects reporting chest pain, shortness of breath or neurologicfal symptoms or other potential indicators of hypertension will have more frequent measurements. Any participant who experiences sustained blood pressure of > 220 systolic or > 120 diastolic or heart rate > 75% predicted maximum during the first experimental session will not be given a second experimental session.

In case of need, subjects will be transferred to the emergency room at Assaf Harofeh Hospital. Subjects who are transferred will be accompanied by a physician or paramedic from the ICU of Maguen David Adom. Reasons for moving a patient to an ICU would include, but not be limited to, severe headache in the setting of hypertension, angina or neurological deficits regardless of blood pressure. In the case of an emergency, intravenous anti-hypertensive agents will be available in addition to the usual resuscitation drugs and equipment. The investigator and co-therapists may, at any time, make a clinical judgment to transfer the patient to the ICU for closer monitoring and additional treatment.

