7.2.3 Body Temperature

MDMA administered in a controlled setting produces only a slight increase in body temperature [68], and ambient temperature does not enhance or attenuate this slight elevation in humans.

If temperature rises more than 1° C, attempts will be made to lower it by removing blankets and layers of clothing, decreasing the ambient temperature and, if necessary, directing a fan toward the participant. If at any time the temperature rises more than 1.5° C above baseline despite these efforts, ice packs will be used, blood will be drawn for stat CBC, electrolytes, BUN/creatinine, glucose, CPK, PT, PTT, platelets and liver enzymes, and urine will be collected for urinalysis.

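### The supplemental dose has no written hold rule: limits that bar a second session weeks later, and the temperature trigger, are not applied to the second capsule the same day

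*Protocol*

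**What the plan says.** Protocol 5.2.3, item u: the half-size supplement "may be administered approximately 1.5 to 2.5 hours after the initial dose upon mutual agreement between the therapists and subject". Table 4 places it at 11:30, in the same row as a blood pressure and pulse reading: "Can administer optional supplemental dose". Section 6.2 also presents it as something that may or may not follow the first dose. Section 2.4 expects it to lengthen the subjective effect without pushing physiological effects above the first peak.

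The in-session limits are set out separately:

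- **Item o (5.2.3):** "More frequent measures will be taken if the established thresholds of 160 systolic, 110 diastolic or pulse 110 are exceeded". Readings are then taken every five minutes until values drop below the thresholds, have been falling for 15 minutes, or "have stabilized at a level judged by the investigator to be safe".
- **Section 7.2.1:** the blood pressure limit is "sustained blood pressure of > 220 systolic or > 120 diastolic". It carries the same bar as the pulse limit, under which a participant with "heart rate > 75% predicted maximum during the first experimental session will not be given a second experimental session".
- **Section 7.2.6:** signs of toxicity, or clinically significant dilutional hyponatremia, after the first session also rule out a second session.
- **Section 7.2.3:** once temperature is more than 1.5 °C "above baseline despite these efforts, ice packs will be used", with stat blood tests and urinalysis.
- **Section 7.2.1, symptoms:** chest pain, shortness of breath or neurological symptoms "or other potential indicators of hypertension will have more frequent measurements". Later text in 7.2.1 goes further. A neurological deficit requires oxygen, an IV and transport to the emergency department. Ischemic-type chest pain requires a stat ECG, oxygen and an IV, with transport if needed.

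**The concern.** The sponsor has already decided that certain responses to a first capsule are reason enough not to give MDMA again. That decision is attached to a session three to five weeks away, when the acute effect is long gone. It is not attached to the second capsule, which falls due while the effect is present.

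Take a hypothetical subject with a sustained 225/122 by 11:30 in the first session. The next session is lost by rule, yet 62.5 mg that same morning stays within protocol if the therapists agree. A subject 1.6 °C above baseline despite cooling gets ice packs and stat bloods, and no text says that the supplement is off. At stake is avoidable exposure of an individual subject and consistency between the co-therapist teams. The primary comparison is not at risk.

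**Working it through.** The protocol and SAP state no figure to reproduce here. The check is a comparison of passages, with some counts.

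**1. Conditions on the supplement.** Item u: therapists and subject agree. Table 4: optional. Section 6.2: possible. None carries a reading, symptom or sign as a condition. The first capsule, by contrast, has written gates in items c to f of 5.2.3 (eligibility review, drug screen, pregnancy test, adherence to the restrictions).

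**2. Each limit against its written consequence.**

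| Finding | Section | Written consequence | Written effect on same-day supplement |
|---|---|---|---|
| Above 160 systolic, 110 diastolic or pulse 110 | 5.2.3 o | Five-minute readings | None |
| Sustained >220 systolic, >120 diastolic, or heart rate >75% of predicted maximum, first session | 7.2.1 | No second session | None |
| Toxicity or hyponatremia after first session | 7.2.6 | No second session | None |
| >1.5 °C above baseline despite cooling | 7.2.3 | Ice packs, bloods, urinalysis | None |
| Ischemic-type chest pain | 7.2.1 | ECG, oxygen, IV; transport if needed | None written |
| Neurological deficit | 7.2.1 | Oxygen, IV, transport | None written, but transport ends dosing in practice |

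**3. Timing and size.**

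- Supplement: 62.5 / 125 = 50% of the initial full dose, 1.5 to 2.5 hours later.
- Barred session: 3 × 7 = 21 to 5 × 7 = 35 days later.
- Session without the supplement: 125 / 187.5 = 66.7% of the full regimen.
- Sessions if all three eligible subjects cross over: (2 + 8 + 3) × 2 = 26, of which (2 + 5 + 3) × 2 = 20 are at full dose.

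**4. Data to apply a rule.** From the 10:00 dose to 11:30, Table 4 has three blood pressure and pulse readings (10:30, 11:00, 11:30) and one temperature (11:00). By 12:30 it has five and two. The dosing window of 2.5 − 1.5 = 1 hour leaves room for 60 / 5 = 12 five-minute readings. A short deferral that uses item o's own end-point is therefore workable.

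**5. How often.** The documents give no rate for these limits. The nearest figure is in 7.2.1: under 5% of Phase 1 volunteers went above 140/90, none needing intervention. Assuming that this carries over to screened subjects with PTSD, the 2 + 5 + 3 = 10 full-dose subjects would include fewer than 10 × 0.05 = 0.5 expected above 140/90, and fewer still above 220/120. This bound covers blood pressure only, not temperature, heart rate or toxicity.

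**The case against.** The strongest reply is that the default is no supplement. It is an option, and the therapists veto it by not agreeing. They would be doing so while taking five-minute readings, under a duty in 7.2.1 to evaluate the patient continually, with ICU transfer open to clinical judgment at any time and with power under 5.4 to withdraw a subject. The hypothetical at 225/122 needs clinicians in that position to choose an optional capsule. All of this stands, and it is why the point is modest.

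It does not close the gap. The other party to the agreement has taken MDMA, and 8.2 lists impaired judgment as an expected reaction. Item u does not mention the investigator, whose judgment item o relies on. The expectation in 2.4 is a general one and does not address a subject whose first peak is already at a limit.

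A reader might infer more than the documents support:

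- **That closer reading is the only response between 160 and 220 systolic.** Section 7.2.1 adds continual evaluation, names severe headache with hypertension as a reason for ICU transfer, and provides for intravenous antihypertensives.
- **That chest pain and neurological symptoms lead only to extra measurements.** The mandatory steps later in 7.2.1 contradict this.
- **That second sessions are worse protected on this point.** The 7.2.1 bar is worded for the first session, but no session of either kind has a same-day hold rule.
- **That no hold rule exists anywhere.** The contingency plans, treatment manual and Investigator's Brochure are cited but were not available, and one of them may contain a rule.

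**Conclusion.** In the protocol and SAP, agreement is the only written condition for the supplement, and none of the limits in 7.2.1, 7.2.3 or 7.2.6 is applied to it in any session. That allows, on protocol, up to 62.5 mg within hours of a response that the protocol elsewhere treats as reason not to dose again. The gap is in the rule. The documents do not show that the team would dose such a subject.

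The event is probably rare, on the assumption that the Phase 1 blood pressure figure is a fair guide. The practical reach is narrowed further because a limit may first be crossed after the supplement. The protocol also does not define how long a reading must last to count as sustained. This is a cheap safety improvement to consider.

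**What to change.** State in item u and Table 4 that in every session, including second sessions and Stage 2, the supplement is not given if:

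1. a 7.2.1 blood pressure or heart rate limit has been reached;
2. temperature is more than 1.5 °C above baseline despite cooling; or
3. there is ischemic-type chest pain, shortness of breath, a neurological deficit or confusion beyond what MDMA would explain, or clinically significant toxicity or hyponatremia.

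Say explicitly that the expected reactions in 8.2 (dizziness, impaired gait, paresthesias, nystagmus and the rest) are not a reason to hold. Otherwise item 3 would stop the supplement for ordinary drug effects.

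If the reading just before the supplement is above 160 systolic, 110 diastolic or pulse 110, defer it within the 2.5-hour window until item o's end-point is met. If the window closes first, omit it. A temperature alongside the 11:30 reading would help but is optional, since item m already provides roughly hourly readings.

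Record given, declined or held, with the reason, and report it by arm beside the dose timing and total mg in SAP 9.6. Keep the analysis by assigned arm.

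Cost: one paragraph and one CRF field. A few full-dose sessions may stop at 125 mg. That slightly affects comparability with the earlier studies cited in 2.4 and the pooling intended in 12.1. Holds would fall mainly on the full-dose arm and may hint at assignment, although the therapists already see the vital signs.

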5.2.4 Integrative Sessions 24 Hours after Experimental Session (Visits 5 and 9)

- a. On the morning after each experimental session, both of the therapists from the subject's team will meet with the subject during a 90-minute integrative therapy session.
- b. The entire integrative psychotherapy session will be recorded to audio and video. Subjects may receive copies of this session upon request.
- c. Subjects will complete the C-SSRS just prior to beginning each integrative session.
- d. Prior to integrative psychotherapy, the subject and both therapists will indicate their beliefs concerning subject condition assignment.
- e. Discuss and review events that occurred with the subject during the integrative session, including thoughts, feelings and memories. If necessary, the therapists will help the subject to reduce any residual psychological distress he or she is

- experiencing. The therapists will also encourage the transfer of states of acceptance, feelings of intimacy, closeness and reduced fear experienced in experimental sessions to emotionally threatening everyday situations. The therapists will be supportive, validating the experience and facilitating understanding and emotional clearing.
- f. The therapists will remain accessible any time the subject needs support outside the scheduled integration sessions.
- g. Assess the subject's mental health and the presence of any remaining reactions during integrative psychotherapy immediately after each experimental session.
- h. Integrative psychotherapy sessions can also serve as an opportunity for the therapists to gather information about the effects of the drug on the subject in an unstructured manner.
- i. After the integrative psychotherapy sessions, a person previously selected by the subject will provide a ride home to the subject. If the subject is unable to locate an individual willing or able to take him or her home, or if the designated person is unable to assist the subject due to unforeseen events, the therapists will assist the subject in finding an alternative means of returning home.
- j. Spontaneously reported reactions, Adverse Events and Medications will be collected as described in Sections 8.5 and 9.0 of the protocol.
- k. Remind the subjects that they will have daily contact for the next 7 days.

5.2.5 Daily Telephone Contact for Seven days after an Experimental Session

- a. Starting on the day of the integrative psychotherapy session following each experimental session, one of the therapists will contact the subject via telephone or in person on a daily basis for one week.
- b. The integrative contact will be for a brief check-in lasting 5 to 15 minutes, or as long as necessary to address any subject's concerns and to assess subject's well-being. Additional telephone contact can be initiated at the request of the therapists or subject.
- c. On the second and seventh day of contact after the experimental session, the subject will complete the C-SSRS.
- d. General wellbeing will be assessed at each phone call.
- e. Spontaneously reported reactions, AEs and Medications will be collected as described in Sections 8.5 and 9.0 of the protocol.

5.2.6 Integrative Psychotherapy Between Experimental Sessions (Visits 6, 7, 10 and 11)

- a. The subject will have two additional integrative psychotherapy sessions lasting at least an hour with at least one of the therapists from the subject's therapist team between each experimental session. The therapists may conduct more sessions if they and the subject deem it necessary.
- b. Record each integrative session to audio and video. Subjects may receive a copy of one or more integrative sessions upon request.

- c. The C-SSRS will be administered just prior to beginning each integrative session.
- d. General wellbeing will be assessed at each integrative session.
- e. The subject will complete the PDS questionnaire on the third integrative session.
- f. The subject and therapists will continue to work on supporting the subject as she or he considers his or her experiences during experimental sessions.
- g. The therapists will use clinical judgment to assess the subject's psychological wellbeing during this period of time. If there are any indications of continuing anxiety or distress, the therapists may arrange to work on reducing the distress at a specially scheduled integrative therapy session, through continuing contact, or at the next regularly scheduled integrative therapy session. The subject may also initiate contact with the therapists at any time throughout the study.
- h. AEs and medications will be collected as described in Sections 8.5 and 9.0 of the protocol.
- i. If an integrative session falls within the period of telephone contact and additional phone call is not required that day, all things normally collected during the telephone call will be completed in person.

5.2.7 Evaluation at End of Stage 1 and Unblinding (Visit 12)

The final evaluation in Stage 1 will occur two months after the second experimental session. This visit will consist of two meetings that may be completed on separate days, one with the independent rater and the other with the therapists.

- a. Subjects will meet the independent rater for at least an hour and a half.
- b. The blinded independent rater will administer:
 - CAPS to assess PTSD symptoms
 - PDS to assess self-reported PTSD symptoms
 - BDI-II to assess depression symptoms
 - GAF to assess general psychological function
 - PSQI to assess sleep quality
- c. The blinded independent rater will provide their belief of the subject's condition.
- d. After completing all assessments and measures with the independent rater, the subject will meet with the therapists for approximately 30 minutes.
- e. The therapists will assess suicidality with the C-SSRS.
- f. General wellbeing will be assessed.
- g. The blind will be broken for the subject's condition assignment. The independent rater will remain blind to condition assignment at this time.
- h. If the subject has received active placebo dose MDMA in Stage 1, the therapists will discuss enrollment in Stage 2. (See section 5.2.8)
- i. If the subject has received full dose MDMA in Stage 1 or the open label lead-in, or they elect not to participate in Stage 2, they will complete the Responses to Research Participation Questionnaire (RRPQ) and continue on to the 12-month Follow Up visit and study termination.
- j. Subjects who are not enrolled in Stage 2 may return to taking psychiatric medications if necessary.
- k. Subjects not enrolled in Stage 2 will receive a memory aid card for use between

this visit and the 12-month follow up. Subjects will use this card to record AEs, medications, and changes in psychiatric status that they will be asked about at the termination visit. Memory Aids will not be collected.

1. AEs and medications will be collected as described in Sections 8.5 and 9.0 of the protocol.

